14 STATISTICAL ANALYSIS METHODS

The methods of analysis to be used for both objectives of the study and for description of the study variables are detailed below.

Quantitative variables will be described with measures of central tendency and dispersion: mean, median, SD (standard deviation), Q1 (first quartile) and Q3 (third quartile), minimum and maximum. Qualitative variables will be described using absolute and relative frequencies.

In the descriptive analysis of qualitative variables, two percentage columns will be presented, total percentage (%) and valid percentage (% valid), that are respectively, the percentage over the sum of valid responses plus missing values and the percentage over the total of valid responses.

For independent samples, parametric (t-test) or non-parametric (Mann-Whitney) statistical tests will be performed, depending on the distribution of the sample.

These tests will be used in all bilateral cases and with a level of significance of 0.048. In cases where a p-value less than 0.048 appears, it refers to the existence of statistical significance.

Clopper-Pearson confidence intervals will be shown at 95.2%.

Data will be analysed using SPSS v29.0.

An interim analysis, not planned at the start of the study, was performed after at least 20 subjects will be enrolled and completed the “Bone Consolidation” event.

The aim of this interim analysis was to verify the consistency of testing hypothesis and to confirm the historical data on the medical device safety and performance. Interim results were used to prepare the Clinical Evaluation Report (CER).

To preserve the integrity of the study results interpretation, a correction for multiplicity due to two planned analyses (interim+final) was implemented using the approach proposed by O'Brian-Fleming for sequential design (Shein –Chung Chow et Al Sample size calculations in Clinical Research 2003, Christopher Jennison et Al Group Sequential Methods with applications to clinical Trials,2000)

For this purpose, sample size was recalculated using this approach (all details are reported in the cited bibliography):

- The initial sample size was correct by factor 1.008 for a twosided test at 5% level and 80% power. The final sample size is $30 * 1.008 = 30.2$
- The probability level was corrected by factor 1.977, at interim the P value was 0.0052 while at the final analysis P value will be 0.048.

The corresponding confidence limits were at interim 99.5% and at final analysis 95.2%

In conclusion, applying the O'Brian-Fleming approach to control the type I error no great impact on sample size is observed and integrity of clinical study is preserved from any interpretation bias.

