12.4 General methodology

Clinical data collected throughout this study will be analyzed by descriptive statistics to assess the hypothesis to test and the study objectives. Descriptive statistics will be provided in summary tables according to the type of variable summarized:

- Quantitative variables will be summarized by using n (sample size), arithmetic mean, standard deviation (SD), median, minimum and maximum;
- Categorical variables will be summarized by using frequency distribution and percentages.

Although the clinical performance and the safety of JPS vary with many factors i.e. the primary diagnosis, the anatomical site (tibia and/or femur), the population (pediatric or adult), the concomitant diseases and the quality of the treated bone, no sub-group descriptive statistics will be done due to the limited sample size; data will be processed as whole entity to prevent any interpretation bias.

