17 SURGERY VISIT

17.1 DEVICE APPLICATION SURGERY

The descriptive statistic (Mean, SD, Median, Q₁, Q₃, Min, Max) will be shown for the following continuous variable:

- Duration surgery (hours)

The categorical variables to be described are, N and (%):

- How many plates were applied during this same surgery?
- Plate Size (3.0 mm / 3.5 mm / 5.0 mm)
- 3.0 mm Plate Type (Prox. Fem. 90° - 110° / Prox. Fem. 130°)
- 3.5 mm Plate Type (Prox. Fem. 90° / 120° / Prox. Fem. 130° / Prox. Fem. 140° / Prox. Fem. 150° / Wide Medial Tibia / Narrow Medial Tibia / Anterolateral Tibia / Distal Femur Plate 3.5 mm)
- 5.0 mm Plate Type (Prox. Fem. 90° / 120° / Prox. Fem. 130° / Prox. Fem. 140° / Prox. Fem. 150° / Distal Fem.)
- If '5.0 mm Plate Type' is equal to 'Prox. Fem. 90° / 120°': Plate holes number will be described
- If '3.5 mm Plate Type' is equal to 'Distal Femur Plate 3.5 mm': Plate holes number will be described
- If '5.0 mm Plate Type' is equal to 'Distal Fem.': Plate holes number will be described

The descriptive statistic (Mean, SD, Median, Q₁, Q₃, Min, Max) will be shown for the following continuous variable by the number of plates that were applied during this surgery:

- Duration surgery (hours)

Comparisons will be performed for this variable described above based on the number of plates using T-Student or U Mann Whitney, ANOVA or Kruskal Wallis, depending on the distribution of the variable.

The descriptive statistic (Mean, SD, Median, Q₁, Q₃, Min, Max) will be shown for the following continuous variable by MDD (Yes / No)¹ present in surgery visit:

- Duration surgery (hours)

Comparisons will be performed for this variable described above based on MDD at surgery using T-Student or U Mann Whitney depending on the distribution of the variable.

¹This variable will be obtained from Form MDD Description.

The descriptive statistic (Mean, SD, Median, Q₁, Q₃, Min, Max) will be shown for the following continuous variable by MDD (Yes / No)¹ present in surgery visit for each number of plates were applied during surgery separately:

- Duration surgery (hours)

Comparisons will be performed for this variable described above based on MDD at surgery using T-Student or U Mann Whitney depending on the distribution of the variable.

¹This variable will be obtained from Form MDD Description.

The categorical variable to be described is, N and (%):

- Did the patient receive a blood transfusion? (Yes / No)

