21.2 DEVICE REMOVAL SURGERY INFORMATION

The descriptive statistic (Mean, SD, Median, Q₁, Q₃, Min, Max) will be shown for the following continuous variable:

- Duration surgery

The descriptive statistic (Mean, SD, Median, Q₁, Q₃, Min, Max) will be shown for the following continuous variable by the number of plates were applied during device **application** surgery:

- Duration surgery (hours)

Comparisons will be performed for this variable described above based on the number of plates using T-Student or U Mann Whitney, ANOVA or Kruskal Wallis, depending on the distribution of the variable.

The descriptive statistic (Mean, SD, Median, Q₁, Q₃, Min, Max) will be shown for the following continuous variable by MDD (Yes / No)¹ present in device removal visit:

- Duration surgery (hours)

Comparisons will be performed for this variable described above based on MDD at surgery using T-Student or U Mann Whitney depending on the distribution of the variable.

¹This variable will be obtained from Form MDD Description.

The categorical variable to be described is, N and (%):

- Did the patient receive a blood transfusion? (Yes / No)

The descriptive statistic (Mean, SD, Median, Q₁, Q₃, Min, Max) will be shown for the following continuous variable:

- Radian dose

The categorical variables to be described are, N and (%):

- Post removal AP projection X-Ray
- Post removal ML projection X-Ray

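### SAP 14, 17.1 and 21.2 add significance tests of surgery duration that do not fit the descriptive, whole-sample plan of Protocol 12.4, and judge each at 0.048 with no control across the tests

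*SAP*

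**What the plan says.** Protocol 12.4 commits the study to descriptive statistics. After naming several factors that may influence performance and safety, it states that "no sub-group descriptive statistics will be done due to the limited sample size" and that the data are handled as one body to avoid biased interpretation. It plans no between-group test.

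SAP 14 introduces t-tests or Mann-Whitney tests for independent samples: "These tests will be used in all bilateral cases and with a level of significance of 0.048". It then sets the reading rule: "In cases where a p-value less than 0.048 appears, it refers to the existence of statistical significance".

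The tests themselves are in two places:

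- SAP 17.1 (application surgery): duration by number of plates; duration by MDD yes/no; and duration by MDD "present in surgery visit for each number of plates were applied during surgery separately".
- SAP 21.2 (removal surgery): duration compared "based on the number of plates using T-Student or U Mann Whitney, ANOVA or Kruskal Wallis", and duration by MDD. The grouping for this last test is unclear. The table is by MDD at the removal visit, but the comparison is said to rest on MDD at surgery.

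The only multiplicity provision is in SAP 14: "a correction for multiplicity due to two planned analyses (interim+final) was implemented". The SAP does not call the duration tests exploratory and does not mention Protocol 12.4 as something it departs from.

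**The concern.** If even descriptive sub-group tables are ruled out because the sample is too small, significance tests on those sub-groups do not fit the same plan. The poorest fit is the test of MDD within plate-number strata of a sample capped at 40 implants.

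These are the only group comparisons in the SAP that yield p-values. MDD is itself a safety endpoint, and the study is meant to support the clinical evaluation for the CE mark. Two misreadings are possible. A chance finding that deficiencies or extra plates lengthen surgery could be reported as established. A non-significant MDD comparison with almost no MDDs behind it could be read as reassurance.

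**Working it through.** **1. Where 0.048 comes from.** SAP 14 states: "The probability level was corrected by factor 1.977, at interim the P value was 0.0052 while at the final analysis P value will be 0.048". Two-sided normal levels with constant 1.977 and two equally spaced looks:

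- final: 2 × (1 − Φ(1.977)) = 0.0480
- interim: 2 × (1 − Φ(1.977 × √2)) = 0.0052

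Both figures reproduce. The level therefore corrects one comparison for being examined twice. It does nothing for several comparisons examined once.

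**2. Number of tests.** Application surgery: 1 by plates + 1 by MDD + k by MDD within plate number. Removal surgery: 1 by plates + 1 by MDD. Total 4 + k. The documents do not give k, so I take 1 to 3.

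**3. Chance of at least one false positive if the tests were independent**, 1 − 0.952^m:

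| k | m | chance |
|---|---|---|
| 1 | 5 | 21.8% |
| 2 | 6 | 25.6% |
| 3 | 7 | 29.1% |

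**4. Allowing for overlap.** The overall MDD test and its within-stratum versions use the same durations, and sparse strata may not be testable. I checked this by simulation with no true effect. Assumed settings, none of them from the documents except the sample range: 30 or 40 implants, 2 strata (50/50) or 3 strata (40/40/20), MDD rate 5% to 30%, normal durations, correlation 0.5 between application and removal duration. Monte Carlo error is one to two percentage points.

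| Records | t-test/ANOVA | Mann-Whitney/Kruskal-Wallis |
|---|---|---|
| Independent implants | about 17-27% | about 11-22% |
| Implants from one surgery share one duration but count separately | about 24-51% | about 19-49% |

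The second row matters because SAP 13 analyses by implant and SAP 17.1 records how many plates went in at the same surgery. The SAP does not say whether the duration tables hold one record per implant or one per operation. The upper part of that row comes from the three-strata setting.

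**5. Very few MDDs, Mann-Whitney branch.** With one MDD among n implants, the smallest exact two-sided p is 2/n:

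- n = 30: 2/30 = 0.067
- n = 40: 2/40 = 0.050

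Both exceed 0.048; n would have to be at least 42 (2/42 = 0.0476). The normal approximation does not help: the largest z is √(3(n−1)/(n+1)), which gives p of about 0.09 at both sizes. With two MDDs in a stratum of m implants the minimum is 4/(m(m−1)): 4/72 = 0.056 at m = 9 and 4/90 = 0.044 at m = 10. A stratum of nine or fewer implants with two MDDs therefore cannot reach 0.048 either.

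**The case against.** Several points on the other side stand.

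- **Scope of Protocol 12.4.** A reader might infer that the protocol expressly forbids these tests. It does not. Its list of factors covers diagnosis, anatomical site, population, concomitant disease and bone quality, and names neither plate number nor MDD. The conflict is with the general wording and with the reason given for it.
- **A single error figure.** A reader might take 26-29% as the error rate. That needs two or three strata, every test estimable, and independence. If only the two plate-number tests could reject, independence gives 1 − 0.952² = 9.4%.
- **One MDD.** A reader might conclude that significance is then impossible. That is true only of the Mann-Whitney branch. A pooled t-test takes its variance from the larger group and rejects in about 5% of null runs. Nor do the documents give an expected MDD rate, so one deficiency cannot be called the likely case.
- **Reach of the 0.048 correction.** A reader might argue that 95.2% should apply only to the primary safety interval. SAP 14 applies it to Clopper-Pearson intervals generally, and nothing here argues against that.
- **Timing.** The SAP describes the interim in the past tense. That does not show that interim results prompted the duration tests.
- **Consequence.** Duration feeds no endpoint and no stated decision. Side analyses in an uncontrolled observational study often go without multiplicity control.

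The last point would settle the matter if the SAP labelled the tests exploratory. Instead it gives a rule that turns any p below 0.048 into a significant finding.

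**Conclusion.** The point holds as a mismatch between protocol and SAP, together with a significance rule that does not deliver the error level it names. Across the duration tests, the chance of at least one false significant result is 22-29% for 5 to 7 independent tests. On the assumed settings with t-tests or ANOVA it is about 17-27% once overlap is allowed for, and about 24-51% if records from one surgery share a duration. Rank tests are lower, particularly when MDDs are rare, but still more than twice 4.8%. These ranges rest on an assumed number of strata, MDD rate and correlation. With very few MDDs, a non-significant Mann-Whitney result is uninformative.

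The primary safety conclusion, the 15% criterion and the efficacy endpoints are not affected. The matter should be corrected, but it does not threaten the study's main result.

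**What to change.** - In SAP 17.1 and 21.2, remove the tests of duration by plate number and by MDD. In SAP 14, remove the sentences that set the 0.048 test level and declare significance for them.
- Report application and removal duration descriptively, and list it individually for operations with an MDD.
- If a breakdown by plate number or MDD is kept, label it descriptive or exploratory with no inference and record it as a departure from Protocol 12.4. State whether each record is an implant or an operation, and settle which visit's MDD defines the groups in SAP 21.2.
- Leave the 95.2% Clopper-Pearson intervals as they are.

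A Bonferroni split (0.048/6 = 0.0080, 0.048/7 = 0.0069) would deal with the number of tests, but not with the departure from Protocol 12.4 or with shared durations.

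The cost is SAP wording and p-values that the protocol did not plan. No endpoint, sample size or data collection changes.

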15 DATABASE LOCK AGREEMENT

If anomalous and/or inconsistent values are detected in any table of results, the database will not be reopened for modification, but instead the anomalous data and the manner in which it was processed will be highlighted (for example, by assigning non-existent data or eliminating the case depending on the statistical method to be used in the analysis in question).

Any modification to this table will be set out in writing in the report, along with the procedure followed (for example, assignment of non-existent data, interpolation, elimination of the case, etc.).

For the final statistical analysis, the database will only be reopened and the study data and tables that could be modified will be re-analysed if, jointly with the sponsor, a rethink of the initial analysis is considered.

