14.2 Monitoring

The sponsor planned to perform a 100% source data verification (SDV), on inclusion/exclusion criteria and on the endpoints variables. On the remaining data the SDV will be performed by random spot check. Before each visit the monitors will contact the investigator/centre to schedule the visit and will send a written confirmation and the related agenda.

In order to fulfill its responsibility of assuring the proper conduct of the study regarding adherence to the CIP and the completeness and accuracy of the data recorded on the case report forms, the sponsor planned to perform at least the following monitoring visits:

- Site Initiation Visit (SIV), to be performed after EC approval;
- 6 monitoring visits throughout the life phase of the study and according monitoring plan;
- Close Out Visit (COV), after the last patient's data are entered into eCRF.

In case of need the investigational site is subjected to additional monitoring visits. The Investigator and/or study staff will be expected to be available for at least a portion of the monitoring visit to answer questions and to provide any missing information.

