14.7 Clinical Study Report

The clinical study report shall be completed by the sponsor, or a designed delegate by the means of a non-disclosure agreement, even if the clinical investigation will be terminated prematurely, only after:

- all queries concerning the eCRF will be closed;
- the database will be locked;
- the statistical report will be written and approved.

The sponsor will draft the clinical study report within 2 months after the statistical report will be finalized. That report will be reviewed and approved by the investigator and, as soon as available, shall be provided to the relevant IEC/IRB, to the regulatory authorities (when applicable). For all statistical details related to Interim Analyses please refer to section 12.5.

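### SAP 15 lets values judged anomalous in the result tables be replaced, or the case dropped, with no check against source and no exemption for the primary endpoint

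*SAP*

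**What the plan says.** SAP 15 (Database lock agreement) starts from a point at which results have been tabulated: "If anomalous and/or inconsistent values are detected in any table of results, the database will not be reopened for modification". The anomalous data and the way they were processed are to be highlighted instead. Processing is illustrated by "by assigning non-existent data or eliminating the case depending on the statistical method to be used in the analysis in question". The second paragraph gives a longer, open-ended list: "assignment of non-existent data, interpolation, elimination of the case, etc".

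Two provisions limit the rule. Disclosure is mandatory: "Any modification to this table will be set out in writing in the report". For the final analysis the database may be reopened and affected tables re-run, but only if "jointly with the sponsor, a rethink of the initial analysis is considered".

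The section does not define what makes a value anomalous. It sets no separate rule for endpoint variables, and requires neither a comparison with source nor an analysis with and without the affected case.

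Elsewhere, Protocol 14.2 plans "100% source data verification (SDV), on inclusion/exclusion criteria and on the endpoints variables". Protocol 14.7 lists, among the conditions for completing the study report, that "all queries concerning the eCRF will be closed" and that the database is locked. SAP 13 defines the analysis set by the eligibility criteria alone.

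**The concern.** The rule operates after the tables exist, so whoever decides that a value is anomalous can already see the outcome. The analysis population in SAP 13 depends only on eligibility. SAP 15 adds another way out of an analysis, with no criterion attached and with outcomes visible.

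The true value can usually be looked up. This is a chart-based study at one site, and the endpoint variables are meant to be fully source-verified. Replacing a value or setting the case aside, where source could settle the matter, is a poor default. Disclosure lets a reader see the change, but the altered estimate remains the reported one.

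With about 30 patients and few expected events, one patient more or less can move the exact upper limit by several percentage points. The study is intended to confirm the benefit/risk ratio and support the CE mark, so the primary proportion should not depend on an undefined post-lock judgement.

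**Working it through.** **Inputs**
- Interval: SAP 14 states "Clopper-Pearson confidence intervals will be shown at 95.2" per cent. The level follows from the final-analysis constant of 1.977: 2 × (1 − Φ(1.977)) = 0.0480, so each tail holds 0.024.
- Reference bound: 15 %, the top of the state-of-art range of 5.1 % to 15.0 % (Protocol 12.1). It is applied to the upper confidence limit in the sample-size assumption.
- Planned size: 30 subjects at an expected proportion of 3 % (Protocol 12.2), or 0.03 × 30 = 0.9 events, so about one. The cap is 40 implant cases (Protocol synopsis, SAP 9).

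**Formula.** The exact upper limit for x events in n is the value p at which P(X ≤ x | n, p) equals the tail area. For x = 0 this is 1 − tail^(1/n). For x = 1 it solves (1 − p)^n + n·p·(1 − p)^(n−1) = tail.

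**The plan's own figure.** With 1/30 and a tail of 0.05 (one-sided 95 %), the limit is 14.86 %, and 30 is the smallest n at which one event stays within 15 %. So N = 30 is reproduced on a one-sided limit. On two-sided limits 1/30 gives 17.22 % at 95 % and 17.35 % at 95.2 %; the smallest n with one event is then 35 and 36 respectively.

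**Effect of one altered case, two-sided 95.2 %**

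| Handling | x/n | Upper limit | Within 15 %? |
|---|---|---|---|
| Event confirmed, patient kept | 1/30 | 17.35 % | No |
| Case eliminated | 0/29 | 1 − 0.024^(1/29) = 12.07 % | Yes |
| Event recoded as no event | 0/30 | 1 − 0.024^(1/30) = 11.69 % | Yes |
| Cap, all kept (40 cases taken as 40 subjects) | 2/40 | 17.03 % | No |
| Cap, one event case eliminated | 1/39 | 13.58 % | Yes |

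**Where it applies.** On this limit only zero events stays within 15 % for n = 23 to 35; at most one event does for n = 36 to 40. Removing one event case changes the reading of a count one above the allowed number for n = 24 to 35 and n = 37 to 40. At n = 36 it does not, because 2/36 becomes 1/35 with a limit of 15.04 %. There the opposite can happen: dropping an event-free case turns 1/36 (14.64 %) into 1/35 (15.04 %).

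**On the one-sided 95 % limit.** Here 1/30 (14.86 %) is already within 15 %, so eliminating the event case changes nothing. The sensitive points move elsewhere: 2/31 is above 15 % and becomes 1/30 (14.86 %) if an event case is dropped, and 1/30 becomes 1/29, above 15 %, if an event-free case is dropped.

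**How often the count is at the sensitive value (n = 30, two-sided 95.2 %).** The chance of exactly one event patient is 30 × 0.03 × 0.97^29 = 37.2 % at a true rate of 3 %, 33.5 % at 5.1 % and 4.0 % at 15 %. If that patient were always removed, the chance of a limit within 15 % would rise from 40.1 % to 77.3 % at 3 %, from 20.8 % to 54.3 % at 5.1 %, and from 0.8 % to 4.8 % at 15 %. These figures are ceilings. They say nothing about how often such a record would be judged anomalous.

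**The case against.** Several things can be said for the plan, and most have substance.

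- **The rule does not order deletion or invention.** Both are introduced as examples; what is required is flagging and written disclosure. That is correct. Assigning non-existent data may also mean setting the value to missing, and SAP 14 reports percentages both with and without missing values. Even so, a missing value leaves the valid-percentage denominator, and interpolation is named separately, although it hardly suits a yes/no variable.
- **A reopening route exists.** It does. It is discretionary, however, and rests on rethinking the analysis rather than on finding an error in source.
- **Errors should be caught before lock.** Full source verification of endpoints and closed queries make late anomalies less likely, but they do not govern those that still appear in the tables.
- **A reader could reverse the change.** SAP 23.1.4 lists all adverse events, SAP 16.1 reports non-evaluable patients with reasons, and modifications are disclosed. This limits concealment; the headline estimate would still be the altered one.
- **A closed database is itself a protection.** This is fair: an unlock after results are seen needs tight limits.

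A reader might infer that one deletion would reverse the primary conclusion. The documents do not support that as a general statement. The 15 % limit is introduced only for sizing the study, the hypothesis is to be assessed descriptively (Protocol 12.4), and the SAP states no pass/fail rule. The example also requires the event record itself to be judged anomalous and its patient removed, and it disappears on the one-sided limit that reproduces N = 30. Nor does anything in the documents suggest that the rule has been or would be misused.

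**Conclusion.** The concern holds in a limited form. SAP 15 permits undefined, outcome-visible handling of any variable, including the primary endpoint, without a check against source; its reopening clause is not tied to a confirmed error. This is more than missing detail, because following the rule as written can bias the primary proportion.

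The size is a conditional worst case: an upper limit of 17.4 % (1/30) against 12.1 % (0/29). It assumes the two-sided 95.2 % exact interval, one implant per patient, 15 % used as the criterion, and an affected case that carries the only event. Part of this sensitivity comes from the small sample rather than from the lock rule. Mandatory disclosure reduces the harm but does not remove it.

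**What to change.** Amend SAP 15 as follows.

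1. Check anomalies in adverse event, causality, device deficiency, consolidation and correction variables against source. Correct confirmed errors through a documented, controlled unlock with an audit trail, limited to those errors.
2. Drop no evaluable patient from the primary analysis because of an anomaly found after lock.
3. If a value cannot be resolved, keep the patient and show the primary result under best-case and worst-case values, or with and without the case.

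The cost is a few sentences of SAP text and, if the rule is ever used, a short unlock of a database of at most 40 cases. The downside is that the unlock would take place after results have been seen; restricting it to source-confirmed errors and recording each change keeps that risk small.

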12. STATISTICS

12.1 Hypothesis

Hypothesis to test:

the observed primary safety endpoint for JPS ranges within the state-of-art (SOA) safety profile of equivalent plating systems.

State of art:

The proportion of subjects with serious/not serious adverse event surely or possibly related to the device reported in the scientific literature for the treatment of congenital deformities and fractures in lower limb of pediatric patients by the means of equivalent plating systems is between 5.1 % and 15.0 % depending on many factors, mainly the diversity of the primary diagnosis.

Assumption:

for the sole purpose of the sample size calculation, it was required to assume an expected proportion for the primary safety endpoint of JPS. The sample size, therefore, was calculated estimating the required number of subjects (considering the case the each patient contributes for only one JPS implant) so that the upper limit of the 95 % confidence interval for the expected proportion is ranged within the SOA (i.e. 95 % CI upper limit \leq 15 %).

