9 STUDY POPULATION

This study will be conducted only on patients with a regular indication for JPS as per IFU (no off-label use will be included): the system is intended in pediatric (excluding newborns) and small stature adult patients. Pediatric patients include infants (greater than 1 month to 1 years of age), children (greater than 1 to 12 years of age) and adolescents (greater than 12 to 18 years of age) and appropriate adults (where according to investigator assessment, the JPS plates fit the treated bone anatomy).

This study includes only one site (monocentric) that is located in Wetter (Germany). The site was chosen for this study due to the number of subject devices already implanted, and the wideness of the indications covered by the surgeries. The site was also positively evaluated by sponsor for the appropriate qualification and competency of the investigator and of the staff, and availability of facilities and equipment.

Sample size calculation:

Assuming the expected proportion of patients with at least one serious/not serious adverse event surely or possibly related to JPS will be 3 %, and assuming the worst case of each patient contributing for only one JPS implant case: 30 subjects was calculated to be the sample size of this study so that the upper limit of the 95 % confidence interval for the primary endpoint, based on the exact binomial method, is under 15 %. Considering that one patient can contribute for one that one JPS implant, and considering a 10% drop out rate, the site can enrol a maximum of 40 JPS implant cases.

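### SAP 15 lets the final data be reopened and re-analysed on a joint rethink with the sponsor after results exist, with no data error required and no rule on which result stands

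*SAP*

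**What the plan says.** SAP 15 has three paragraphs. The first keeps the database closed when anomalous or inconsistent values turn up in a results table; the analyst instead flags them and how they were treated, which may include setting them to missing or dropping the case. The second adds: "Any modification to this table will be set out in writing in the report, along with the procedure followed". The third concerns the final analysis. It limits reopening to one situation, in which the affected material "will be re-analysed if, jointly with the sponsor, a rethink of the initial analysis is considered".

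SAP 14 corrects for two analyses, one interim and one final, at levels 0.0052 and 0.048. It states that "Clopper-Pearson confidence intervals will be shown at 95.2"%, and concludes that "integrity of clinical study is preserved from any interpretation bias".

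The 15% figure comes from the sizing. SAP 9 sets 30 subjects with this target: "the upper limit of the 95 % confidence interval for the primary endpoint, based on the exact binomial method, is under 15"%. Protocol 12.1 names a hypothesis, that the observed primary safety endpoint lies within the state-of-the-art range (5.1% to 15.0%), and describes the sizing as done "so that the upper limit of the 95 % confidence interval for the expected proportion is ranged within the SOA".

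Neither document says whether the first locked result or a later one is the study result. Neither requires independent approval of a reopening or limits how often it may happen. Protocol 14.7 asks for closed queries, a locked database and an approved statistical report before the study report, and is silent on unlocking.

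**The concern.** The third paragraph of SAP 15 presupposes that an analysis has been run and seen. The only stated trigger for reopening is a change of mind about that analysis, shared with the sponsor. A suspect value, the usual reason to unlock, is the case for which the first paragraph keeps the database closed.

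The study is uncontrolled, so anyone who sees the data can see which way a change would move the result. The endpoint depends on a judgement of relatedness, which Protocol 11.1.3 assigns to both investigator and sponsor. The results are meant to support keeping the CE mark (Protocol 5.2). At this sample size one event decides on which side of 15% the upper limit falls. A reader of the report would need to know whether the figure shown is the planned analysis or one chosen after it, and the SAP does not ensure that.

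**Working it through.** **1. What the stated error control covers.** Inputs from SAP 14: O'Brien-Fleming constant 1.977, two analyses.

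- Interim: p = 2[1 − Φ(1.977 × √2)] = 0.00518 (SAP: 0.0052).
- Final: p = 2[1 − Φ(1.977)] = 0.04804 (SAP: 0.048).
- Overall two-sided error from the bivariate normal: 0.0501 with equally spaced looks, 0.0490 if the interim falls at 20 of 30.

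The plan's levels reproduce. They use essentially the whole 5%, so nothing is set aside for a second final analysis.

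**2. Where the 15% limit falls.** Exact upper limit at 95.2% (2.4% per side): the 0.976 quantile of Beta(x + 1, n − x).

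| Events / N | 95.2% upper limit | At or below 15%? |
|---|---|---|
| 0/30 | 11.69% | yes |
| 1/30 | 17.35% | no |
| 1/36 | 14.64% | yes |
| 2/36 | 18.79% | no |
| 1/40 | 13.26% | yes |
| 2/40 | 17.03% | no |

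At N = 30, a first result of 1 event misses. Reclassifying that event gives 0/30 (11.69%), and dropping the subject gives 0/29 (12.07%); both pass.

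The planned N = 30 itself reproduces with 1 event (3% of 30 = 0.9, rounded) only on a one-sided 95% limit, 14.86%; the two-sided 95% limit is 17.22%. On the one-sided version 1/30 passes and 2/30 (19.53%) fails, so one event still separates the two readings.

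**3. Illustration of the effect.** Assume a true rate of 15%, the 95.2% limit read as pass or fail against 15%, and, as a worst case, every miss by exactly one event turned into a pass. With c the largest number of events that passes, the chance of passing goes from P(X ≤ c) to P(X ≤ c + 1), X binomial(N, 0.15).

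For N = 30, c = 0: P(X = 0) = 0.85^30 = 0.0076. Adding P(X = 1) = 30 × 0.15 × 0.85^29 = 0.0404 gives 0.0480.

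| N | c | Planned analysis | After removing one event |
|---|---|---|---|
| 30 | 0 | 0.8% | 4.8% |
| 34 | 0 | 0.4% | 2.8% |
| 35 | 0 | 0.3% | 2.4% |
| 36 | 1 | 2.1% | 7.8% |
| 40 | 1 | 1.2% | 4.9% |

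The reference is the nominal 2.4% per side. The figure jumps at 36 because that is the first N at which one event passes.

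**4. How often the question would arise.** At the plan's own 3% rate and N = 30, the chance of exactly one event is 30 × 0.03 × 0.97^29 = 0.372. A miss by one event would be an ordinary outcome.

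**The case against.** The strongest reply is that the third paragraph restricts: the word *only* limits reopening, and the sentence follows two paragraphs about anomalous values. It could be read as a jointly agreed exception to the closed-database rule. That reading is possible, but it does not supply a trigger. Even as an exception, what is named is a rethink of the analysis, not an error in the data, and the question of which result stands remains open.

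A reader might infer more: that the plan allows the 15% criterion to be tested twice and has therefore lost type I error control. The documents do not support that.

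- They state no pass/fail rule for the final analysis. The 15% limit sits in the sizing assumption, Protocol 12.4 assesses the hypothesis by descriptive statistics, and SAP 23 only displays proportions with intervals.
- A re-analysis of largely the same data is not an independent second test, and no document gives a basis for its frequency or direction.
- The largest figure, 7.8% at N = 36, is a peak. It should not be quoted alone: the planned number is 30 subjects, and at 35 the same assumption ends at the nominal 2.4%.

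Safeguards also exist. SAP 23.1.3 uses the investigator's assessment of relatedness, endpoint variables get 100% source verification (Protocol 14.2), and eCRF entries must come from source (Protocol 14.6). SAP 15 does not expressly authorise anyone to re-judge events. Its written-record rule gives some transparency, although it refers to table changes for anomalous values and is not clearly extended to reopening. These points make abuse less likely. They do not settle which result is primary after a rethink.

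**Conclusion.** The point holds as a gap in the rules for re-analysis. SAP 15 permits a results-driven re-analysis of the final data on a subjective, sponsor-shared trigger and leaves the status of the planned result undefined. The assurance in SAP 14 that interpretation bias is excluded rests on a correction for two analyses and cannot be extended to this one.

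Its size cannot be established from the documents. What can be shown is sensitivity: at 30 subjects one changed event reverses the reading against 15%, and in the assumed worst case the chance of passing at a true 15% goes from 0.8% to 4.8%. That rests on three assumptions: the sizing limit is read as the criterion, the interval is the 95.2% two-sided one, and every one-event miss is removed. It does not demonstrate that type I error control is lost or that such re-analysis is intended. An inexpensive correction to the SAP is warranted.

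**What to change.** Replace the last paragraph of SAP 15 with wording such as:

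> The database is reopened only to correct a documented error against source data, with reason, approval and audit trail. The planned SAP analysis is then rerun unchanged on the corrected data, and the results before and after correction are both reported. Any change to the analysis method, the analysis set or the classification of events made after results were seen, other than such a correction, and including elimination of a case or assignment of values under paragraph 1, is labelled post hoc, reported beside the planned analysis, and does not replace it for the primary endpoint.

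Paragraph 1 must be aligned. As written it bars reopening for anomalous values, which would conflict with correcting a source error. It also allows a case to be dropped after results tables are seen, which has the same effect without any reopening.

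It would be wrong simply to declare the first locked result final: a device-related event missed in transcription must be able to change the primary safety result. The wording above allows that.

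The cost is a text change, with no new data or subjects. The sponsor gives up the option of replacing the planned result with a revised one, but exploratory re-analysis remains possible if labelled as such.
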